3.1.2 Mechanism of Action

The active moiety of Radium Ra-223 dichloride is the alpha particle-emitting isotope Radium-223 (as radium Ra-223 dichloride), which mimics calcium and forms complexes with the bone mineral hydroxyapatite at areas of increased bone turnover, such as bone metastases. The high linear energy transfer of alpha emitters (80 keV/micrometer) leads to a high frequency of double-strand DNA breaks in adjacent cells, resulting in an anti-tumor effect on bone metastases. The alpha particle range from Radium-223 dichloride is less than 100 micrometers (less than 10 cell diameters) which limits damage to the surrounding normal tissue.

3.1.3 Preclinical

In single and repeated dose toxicity studies in rats, the main findings were reduced body weight gain, hematological changes, reduced serum alkaline phosphatase and microscopic findings in the bone marrow (depletion of hematopoietic cells, fibrosis), spleen (secondary extra-medullary hematopoiesis) and bone (depletion of osteocytes, osteoblasts, osteoclasts, fibro-osseous lesions,

disruption/disorganization of the physis/growth line). These findings were related to radiation-induced impairment of hematopoiesis and a reduction of osteogenesis and occurred beginning in the dose range of 20 (0.00056 mCi) – 80 kBq (0.0022 mCi) per kg body weight, with the exception of body weight decreases.

Dose-limiting myelotoxicity was seen in dogs after single administration of 450 kBq (0.012 mCi) Radium Ra-223 dichloride per kg body weight (9 times the clinically recommended dose).

Osteosarcomas, a known effect of bone-seeking radionuclides, were observed at clinically relevant doses in rats 7 to 12 months after start of treatment.

Osteosarcomas were not observed in dog studies. The presence of neoplastic changes, other than osteosarcomas, was also reported in the longer term (12 to 15 months) rat toxicity studies. Due to its mode of action, and as seen with conventional radiotherapy and other radiotherapeutics, Radium-223 dichloride may have the potential to induce secondary malignancies. No case of osteosarcoma has been reported in clinical studies with Radium Ra-223 dichloride. The risk for patients to develop osteosarcomas with exposure to Radium Ra-223 dichloride is unknown at present.

Studies on reproductive and developmental toxicity have not been performed. Since Radium Ra-223 dichloride binds to bone, the potential risk for toxic effects in the male gonads in cancer patients with castration-resistant prostate cancer is very low, but cannot be excluded. Studies on the mutagenic and carcinogenic potential of Radium Ra-223 dichloride have not been performed.

No histological changes were observed in organs involved in the excretion of Radium Ra-223 dichloride. No significant effects were seen on vital organ systems, i.e., cardiovascular (dog), respiratory or central nervous systems (rat), after single dose administration of 450 to 1000 kBq (0.012 to 0.027 mCi) per kg body weight (9 (dog) to 20 (rat) times the clinically recommended dose.

3.1.4 Clinical Experience Summary

The clinical development of Radium Ra-223 dichloride includes phase I and phase II studies in prostate cancer patients with bone metastases. The results of these completed studies indicated that safety and tolerability of Radium Ra-223 dichloride in CRPC/HRPC patients with bone metastases was well tolerated, and that there was evidence of dose related efficacy against bone markers and other markers of disease. In addition there was an effect on median overall survival in a Phase II (BC1-02) placebo-controlled study. These studies enabled the initiation of the Phase III ALSYMPACA (ALpharadin in SYMptomatic Prostate CAncer) study.

The clinical safety and efficacy of Radium Ra-223 dichloride have been evaluated in a double-blind, randomized, multiple dose, phase III multicenter study (ALSYMPACA) in castration-resistant prostate cancer patients with bone metastases. The primary efficacy endpoint was Overall Survival (OS).

At the cut-off date of the pre-planned interim analysis, a total of 809 patients were randomized 2:1 to receive Radium Ra-223 dichloride 50 kBq (0.0014 mCi)/kg intravenously every 4 weeks for 6 cycles (N=541) plus best standard of care or matching placebo plus best standard of care (N=268). Best standard of care included e.g., local external beam radiotherapy, corticosteroids, antiandrogens, estrogens, estramustine, or ketoconazole.

An updated descriptive analysis of safety and of OS was performed in 921 randomized patients prior to implementing crossover (i.e., offering patients in the placebo group to receive Radium Ra-223 dichloride treatment).

The results of both, interim and updated analysis, revealed that OS was significantly longer in patients treated with Radium Ra-223 dichloride plus best standard of care compared to patients treated with placebo plus best standard of care. For the updated analysis, an increase in median overall survival of 3.6 months was seen with Radium Ra-223 dichloride plus best standard of care compared to placebo plus best standard of care (HR = 0.695 (95% CI 0.581/0.832), median OS 14.9 months versus 11.3 months, respectively).

In the ALSYMPCA study, the results of the interim analysis and the updated analysis showed also a significant improvement in all main secondary endpoints in the Radium Ra-223 dichloride arm compared to the placebo arm:

- Time to first SRE (defined as time to EBRT, time to first pathological bone fracture, time to spinal cord compression and time to surgical intervention) was statistically significantly longer in the Radium-223 chloride group compared to placebo (median number of months=15.6 for Radium-223 chloride versus 9.8 months for placebo (HR=0.658, 95 CI 0.522–0.830, p= 0.00037).
- Time to total ALP progression (defined as $\geq 25\%$ increase compared to baseline/nadir) was statistically significantly longer in the Radium-223 chloride group 7.4 months compared to placebo 3.8 months (HR = 0.167, 95% CI 0.129 – 0.217; p= <0.00001).
- Time to PSA progression (defined as a $\geq 25\%$ increase and an increase in absolute value of ≥ 2 ng/mL compared to baseline/nadir) was also significantly prolonged in patients receiving Radium Ra-223 dichloride compared to patients receiving placebo (HR = 0.643, 95% CI 0.539,0.768; p = <0.00001)
- A total ALP response (defined as a confirmed $\geq 30\%$ or $\geq 50\%$ reduction compared to baseline) at week 12 was observed in higher proportions of subjects who were treated with Radium-223 chloride group (47% and 3% respectively) compared to those in the placebo (3% and <1% respectively) group.
- Subgroup survival analysis showed a consistent survival benefit for treatment with Radium Ra-223 dichloride, independent of total alkaline phosphatase (ALP), current use of bisphosphonates, prior use of docetaxel and baseline ECOG status. The results from the phase III ALSYMPCA study regarding time to external beam radiation therapy (EBRT) for pain relief and fewer patients reporting bone pain as

an adverse event in the Radium Ra-223 dichloride group indicate a positive effect on bone pain.

The most common adverse reactions ($\geq 10\%$) in patients receiving Radium Ra-223 dichloride were nausea, diarrhea, vomiting, and peripheral edema (Table 2.1). Grade 3 and 4 adverse events were reported among 57% of Radium Ra-223 dichloride-treated patients and 63% of placebo treated patients. The most common hematologic laboratory abnormalities in Radium Ra-223 dichloride-treated patients ($\geq 10\%$) were anemia, lymphocytopenia, leukopenia, thrombocytopenia, and neutropenia (Table 2.2). Treatment discontinuations due to adverse events occurred in 17% of patients who received Radium Ra-223 dichloride and 21% of patients who received placebo.

The most common hematologic laboratory abnormalities leading to discontinuation for Radium Ra-223 dichloride were anemia (2%) and thrombocytopenia (2%).

Table 2.1 shows adverse reactions occurring in $\geq 2\%$ of patients and for which the incidence for Radium Ra-223 dichloride exceeds the incidence for placebo.

Table 2.1: Adverse Reactions in the Randomized Trial

System/Organ Class Preferred Term	Radium Ra-223 dichloride (n=600)		Placebo (n=301)	
	Grades 1-4 %	Grades 3-4 %	Grades 1-4 %	Grades 3-4 %
Blood and lymphatic system disorders				
Pancytopenia	2	1	0	0
Gastrointestinal disorders				
Nausea	36	2	35	2
Diarrhea	25	2	15	2
Vomiting	19	2	14	2
General disorders and administration site conditions				
Peripheral edema	13	2	10	1
Renal and urinary disorders				
Renal failure and impairment	3	1	1	1

Laboratory Abnormalities

Table 2.2 shows hematologic laboratory abnormalities occurring in $> 10\%$ of patients and for which the incidence for Radium Ra-223 dichloride exceeds the incidence for placebo.

Table 2.2: Hematologic Laboratory Abnormalities

Laboratory values were obtained at baseline and prior to each 4-week cycle.

Hematologic	Radium-223 (n=600)		Placebo (n=301)	
	Laboratory	Grades 1-4	Grades 3-4	Grades 1-4
Abnormalities	%	%	%	%
Anemia	93	6	88	6
Lymphocytopenia	72	20	53	7
Leukopenia	35	3	10	<1
Thrombocytopenia	31	3	22	<1
Neutropenia	18	2	5	<1

As an adverse reaction, grade 3-4 thrombocytopenia was reported in 6% of patients on Radium Ra-223 dichloride and in 2% of patients on placebo. Among patients who received Radium Ra-223 dichloride, the laboratory abnormality grade 3-4 thrombocytopenia occurred in 1% of docetaxel naïve patients and in 4% of patients who had received prior docetaxel. Grade 3-4 neutropenia occurred in 1% of docetaxel naïve patients and in 3% of patients who have received prior docetaxel.

Fluid Status

Dehydration occurred in 3% of patients on Radium Ra-223 dichloride and 1% of patients on placebo. Radium Ra-223 dichloride increases adverse reactions such as diarrhea, nausea, and vomiting which may result in dehydration.

Injection Site Reactions

Erythema, pain, and edema at the injection site were reported in 1% of patients on Radium Ra-223 dichloride.

Secondary malignant neoplasms

No cases of radiation-induced cancer have been reported in reported in clinical trials with Radium-223 dichloride in follow-up of up to three years. However, the radiation dose resulting from therapeutic exposure may result in higher incidence of cancer (e.g., sarcomas of the bone, or leukemia), mutations and a potential for development of hereditary defects.

Bone Marrow Suppression

In the randomized trial, 2% of patients on the Radium Ra-223 dichloride arm experienced bone marrow failure or ongoing pancytopenia compared to no patients treated with placebo. There were two deaths due to bone marrow failure and for 7 of 13 patients treated with Radium Ra-223 dichloride, bone marrow failure was ongoing at the time of death. Among the 13 patients who experienced bone marrow failure, 54% required blood transfusions. Four percent (4%) of patients on the Radium Ra-223 dichloride arm and 2% on the placebo arm permanently discontinued therapy due to bone marrow suppression.

In the randomized trial, deaths related to vascular hemorrhage in association with myelosuppression were observed in 1% of Radium Ra-223 dichloride-treated

patients compared to 0.3% of patients treated with placebo. The incidence of infection-related deaths (2%), serious infections (10%), and febrile neutropenia (<1%) were similar for patients treated with Radium Ra-223 dichloride and placebo.

Myelosuppression; notably thrombocytopenia, neutropenia, pancytopenia, and leukopenia; has been reported in patients treated with Radium Ra-223 dichloride. In the randomized trial, complete blood counts (CBCs) were obtained every 4 weeks prior to each dose and the nadir CBCs and times of recovery were not well characterized. In a separate single-dose phase 1 study of Radium Ra-223 dichloride, neutrophil and platelet count nadirs occurred 2 to 3 weeks after Radium Ra-223 dichloride administration at doses that were up to 1 to 5 times the recommended dose, and most patients recovered approximately 6 to 8 weeks after administration.

In the Radium-233 arm of the Phase 3 clinical trial reported in Parker et al. (2013) 12.7% (76/600) of subjects had grade 3+ anemia, 6.5% (39/600) of subjects had grade 3+ thrombocytopenia, and 2.2% (13/600) of subjects had grade 3+ neutropenia.

The safety and efficacy of concomitant chemotherapy with Radium Ra-223 dichloride have not been established. Outside of a clinical trial, concomitant use with chemotherapy is not recommended due to the potential for additive myelosuppression. If chemotherapy, other systemic radioisotopes or hemibody external radiotherapy are administered during the treatment period, Radium Ra-223 dichloride should be discontinued.

3.2 External beam radiation therapy

Radiation therapy will be performed on linear accelerators capable of delivering X-ray or electron therapy in the 4MeV to 18 MeV range with image guidance systems.

4 STUDY DESIGN

4.1 Description

This is a phase IIa, open-label, single-arm, and prospective study of hormone therapy-naïve men with oligometastatic prostate cancer to the bone. The study will test if treating the primary tumor sites and 5 or fewer sites of bone-only metastasis with external beam radiation with concomitant systemic Radium-223 will reduce the utilization of androgen deprivation therapy, improve QOL and improve OS over the comparator cohort of SWOG intermittent ADT historic cohort.

4.2 Number of Patients

20 patients

4.3 Number of Study Centers

This study will be conducted at a single site, the Huntsman Cancer Institute

4.4 Study Duration

The estimated duration for the protocol (from start of screening to last subject processed and finishing the study) is 3 to 4 years (Accrual at 2 patients per month. Study duration will be 6 months per patient. Patient will be followed for approximately 2 years after study enrollment).

5 ELIGIBILITY CRITERIA

This eligibility checklist is used to determine patient eligibility and filed with signature in the patient research chart.

Patient No. _____

Patient's Initials: (L, F, M) _____

5.1 Inclusion Criteria

Yes/No (Response of "no" = patient ineligible)

5.1.1 _____ Asymptomatic or symptomatic hormone naïve men with testosterone levels ≥ 100 ng/dL with previously treated localized prostate cancer who now have rising PSAs and five or fewer bone metastases.

5.1.2 _____ Subjects who have been previously treated with definitive and/or adjuvant/salvage radiotherapy to the primary site and/or regional lymph nodes with concurrent ADT are allowed if the last hormone therapy delivered > 6 months prior. Subjects who have had more than 30 days and fewer than 45 days of bicalutamide monotherapy for any reason within the 6 months prior to enrollment are eligible for the study, providing they have been off of the drug for at least 30 days prior to enrollment. Subjects who have had fewer than 30 days of bicalutamide are eligible for the study, as long as they discontinue the drug at least 5 days prior to the first study treatment.

5.1.3 _____ Histologic confirmation of Prostate Adenocarcinoma diagnosis.

5.1.4 _____ Age ≥ 18 years.

5.1.5 _____ Life expectancy of at least 2 years.

5.1.6 _____ Acceptable hematology and serum biochemistry screening values:

- White Blood Cell Count (WBC) $\geq 3,000/\text{mm}^3$
- Absolute Neutrophil Count (ANC) $\geq 1,500/\text{mm}^3$
- Platelet (PLT) count $\geq 100,000/\text{mm}^3$
- Hemoglobin (HGB) $\geq 10 \text{ g/dL}$
- Total bilirubin level $\leq 1.5 \times$ institutional upper limit of normal (ULN)
- Aspartate aminotransferase (AST) and alanine aminotransferase (ALT) $\leq 2.5 \times$ ULN
- Creatinine $\leq 1.5 \times$ ULN
- Albumin $> 2.5 \text{ mg/dL}$

5.1.7 _____ Willing and able to comply with the protocol, including follow-up visits and examinations.

5.1.8 _____ Karnofsky Performance Score >60 or ECOG equivalent.

5.1.9 Radiographic confirmation of oligometastatic diagnosis via Bone Scan validated by either CT scan, or MRI or PET/CT with Fluciclovine within the past 90 days.

5.1.10 Subjects who have not had surgical removal of their prostate and have a partner of child bearing potential must agree to use condoms beginning at the signing of the ICF until at least 6 months after the last dose of study drug. Because of the potential side effect on spermatogenesis associated with radiation, female partners of childbearing potential must agree to use a highly effective contraceptive method during and for 6 months after completing treatment.

5.1.11 Able to provide informed consent and willing to sign an approved consent form that conforms to federal and institutional guidelines.

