5.2 Exclusion Criteria

Yes/No (Response of “yes” = patient ineligible)

5.2.1 Men with known brain or visceral metastases (except regional lymph nodes as defined by section 5.2.5) defined by CT or MRI Imaging of the abdomen or pelvis.

5.2.2 Men who have had LHRH agonist or antagonist hormone therapy in the prior six months.

5.2.3 Men with >5 validated bony metastases.

5.2.4 Men with baseline serum Testosterone <100 ng/dL.

5.2.5 Men with new or progressing lymphadenopathy clearly consistent with prostate metastasis on imaging or proven by pathologic biopsy at any time three months or later following their initial definitive therapy.

5.2.6 Prior or concurrent invasive malignancy (except non-melanomatous skin cancer) or lymphomatous/hematogenous malignancy unless continually disease free for a minimum of 3 years. All patients with in situ carcinoma are eligible for this study (for example, carcinoma in situ of the oral cavity is eligible) except patients with carcinoma of the bladder (including in situ bladder cancer or superficial bladder cancer).

5.2.7 Use of finasteride within 30 days prior to therapy PSA should not be obtained prior to 30 days after stopping finasteride.

5.2.8 Use of dutasteride within 90 days prior to therapy. PSA should not be obtained prior to 90 days after stopping dutasteride.

5.2.9 Previous or concurrent cytotoxic chemotherapy for prostate cancer.

5.2.10 Received systemic therapy with radionuclides (e.g., strontium-89, samarium-153, rhenium-186, or rhenium-188, or Radium Ra-223 dichloride) for the treatment of bony metastases.

5.2.11 Men who will receive radical prostatectomy to the primary site.

5.2.12 Imminent spinal cord compression based on clinical findings and/or magnetic resonance imaging (MRI). Spinal Cord compression will be defined as 360-degree circumferential obliteration of T2 cerebrospinal fluid signal around the spinal cord. Treatment should be completed for spinal cord compression.

5.2.13 Severe, active co-morbidity, defined as follows:

- Unstable angina and/or congestive heart failure requiring hospitalization within the last 6 months
- Transmural myocardial infarction within the last 6 months
- Acute bacterial or fungal infection requiring intravenous antibiotics at the time of registration
- Chronic obstructive pulmonary disease exacerbation or other respiratory illness requiring hospitalization or precluding study therapy at the time of registration

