7.2 Radium-223

Radium Ra-223 dichloride will be delivered intravenously at 55 kBq (1.49 mCi)/kg (+/- 10% total dose) for a total of six cycles. 1 cycle= 28 days. The first cycle will commence at study enrollment, then cycles 2 through 6 will commence after the completion of radiotherapies at 4-week intervals.

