8.1 Dose Modifications

8.1.1 Dose Modification

Every effort should be made to administer the full dosing regimen of Radium Ra-223 dichloride. Adjustment of dose level is not permitted.

Study visits for administration of Radium-223 during the treatment period should occur at 28 day intervals (within a window of 0 and +14 days). Radium-223 cannot be administered earlier than 28 days from the previous administration. Dosing delays may be instituted under the following circumstances:

Disease progression:

The Investigator should delay cytotoxic chemotherapy, other systemic radioisotope, hemibody external radiotherapy or other investigational drug until the follow-up period. If such treatments have to be given during the treatment period, further study drug administrations must be discontinued.

Patients with a single PSA result that meets biochemical progression criteria may continue on treatment, at the investigator's discretion, until a confirmatory PSA result is returned. Upon confirmed biochemical progression study treatment MUST be discontinued.

Patients who demonstrate radiographic or clinical progression must discontinue study treatment.

Myelosuppression:

Treatment-related changes in hematology parameters may occur.

- If a patient experiences CTCAE v4.03 Grade 3 or 4 neutropenia, thrombocytopenia, or anemia the administration of study drug should be delayed until recovery to Grade 2 or better.
- If a patient experiences CTCAE v4.03 Grade 3 or 4 neutropenia, thrombocytopenia, or anemia lasting > 14 days, further study drug administrations must be discontinued.
- Blood transfusion is acceptable between study drug administrations but not prior to the start of the study. Use of biologic response modifiers, such as G-CSF or GM-CSF, is allowed in the management of acute toxicity.

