9 STUDY CALENDAR

1 cycle = 28 days¹¹

Examination	Screening ¹	Neo-adjuvant C1	EBRT	C2 ⁷	C3	C4	C5	C6	End of Treatment ¹⁷	Follow-up ⁸
Informed consent	X									
Medical history	X									
Eligibility criteria	X									
Vital signs	X	X		X	X	X	X	X	X	
Physical examination ¹⁸	X	X		X	X	X	X	X	X	X
Karnofsky Performance Status or ECOG Equivalent (Appendix 17.5) ¹⁸	X	X		X	X	X	X	X	X	
Concomitant Medications ¹⁸	X	X	X	X	X	X	X	X	X	X
Adverse Events ¹⁴		X	X	X	X	X	X	X	X	X
Hematology ^{2, 13}	X	X ¹³		X ¹³	X					
Chemistry ^{3, 13}	X	X ¹³		X ¹³	X					
ECG ⁵	X									
CT or MRI ⁴	X								X	
Radium-223 ¹⁶		X		X	X	X	X	X		
EBRT			X							
PSA and Testosterone ^{9, 13}	X	X	X ⁹	X	X	X	X	X	X	X
Bone scans ⁶	X			X ¹²	X ¹²	X	X ¹²	X ¹²	X	X
QOL questionnaires	X		X ¹⁵			X			X	X
Myriad CCP ¹⁰	X									
Myriad HRD ¹⁰	X									

- 1 ALL Pre-study/Screening procedures should be completed within 4 weeks of study enrollment - with the exception of laboratory tests which need to be completed within 2 weeks prior to study enrollment, and imaging assessments which must be completed within 90 days of enrollment. Consent may be signed \leq 45 days prior to cycle one day one.
- 2 Hematology includes CBC with differential and platelets.
- 3 Chemistry includes Albumin, Alkaline Phosphatase, Aspartate Aminotransferase, Alanine Aminotransferase, Total Bilirubin, Calcium, Carbon Dioxide, Creatinine, Chloride, Glucose, Potassium, Protein, Sodium, Urea Nitrogen. 4 CT-based scans (either Fluciclovine PET/CT or diagnostic CT) or MRI that includes the chest, abdomen and pelvis. A similar imaging modality (MRI or CT-based) used at screening is preferred, but not required at follow up evaluation. Diagnostic CT at follow-up is sufficient if PET/CT was used at screening. Disease assessment to be conducted by PCWG2 and RECIST 1.1 section 10.1.1.
- 5 ECG will be done only if medically indicated.
- 6 Bone scans should be obtained between cycle 3 and 4 of the study dependent on any dose delays that may extend cycle time. Bone scans should be performed 2-4 weeks after the final Radium-223 dose. Bone scans will also be performed at any sign of progression as defined in section 10.
- 7 Cycle 2 may be delivered concurrently with external beam radiation to the primary site. Therefore, cycle 2 will NOT be delayed to allow completion of the external beam radiation.
- 8 Follow-up visits will occur every 3 months (+90/-30 days) for an approximate duration of two years from the time patients are enrolled on the study.

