- 9 PSA and Testosterone within 24 hours prior to or after starting external beam radiation.
- 10 Correlative studies are OPTIONAL; refer to section 14.1 for archival tissue instruction
- 11 Cycles should occur at least 28 days after the previous cycle and no more than 42 days after the previous cycle (0 to +14 days).
- 12 Bone scans are optional at the time points indicated by this superscript and will be performed if there is clinical suspicion of progression that falls outside the objective criteria of progression for this study.
- 13 All post-screening laboratory tests should be drawn approximately 7 days, but no fewer than 3 business days, before radium dosing. Laboratory tests for CBC differential platelets must have results available prior to radium ordering. Laboratory safety assessments MUST be performed and resulted prior to radium dosing.
- 14 The collection of all adverse events will begin after the first dose of study treatment and end 30 days after the last dose of study treatment. The collection of treatment related adverse events will continue until the last study visit (or until new cancer treatment is initiated, if sooner).
- 15 QOL Questionnaires should be completed on the final day of EBRT \pm 7days.
- 16 If a patient meets biochemical progression, the patient may continue to receive treatment, at the Investigator's discretion, until a validated PSA test has confirmed biochemical progression.
- 17 End of treatment visit will occur 28 days (\pm 7 days) after last treatment is administered.
- 18 Physical exam, KPS or ECOG equivalent, and concomitant medications do not need to be repeated if they have been performed less than 7 days prior.

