10.1 Primary Endpoint – 15 month Hormone Free Survival

The primary objective is to determine the hormone-therapy-free survival time for men treated with sequential EBRT and Radium-223 and determine whether it is a 20% risk reduction over the institutional comparator of 100% use of systemic therapy by 15 months. The primary outcome is 15 months hormone-free survival. Patients will remain on study treatment for the duration defined by the calendar or for disease progression. Patients will be followed up to determine the start of ADT which will be used to measure the primary end point.

For the purposes of this study, progression will be measured after the completion of EBRT and the delivery of Cycle 2 of Radium-223 and defined as either:

Biochemical Progression:

- For those subjects whose PSA is greater than 20ng/ml at baseline who do not have any PSA decrease after starting therapy: biochemical progression will be defined as a 10% rise over the baseline.

- For those subjects whose PSA is greater than 20ng/ml at baseline, who demonstrate decrease in PSA after study treatment: if the PSA nadir remains > 20ng/ml, biochemical progression will be defined as a PSA rise greater than 10% of the PSA nadir. If the PSA nadir is < 20ng/ml, biochemical progression will be defined as a PSA rise greater than 10% of the PSA nadir.

-For those subjects whose PSA is less than 20ng/ml at baseline: biochemical progression will be defined as PSA >20ng/ml and 10%.

*Any PSA test that would meet a failure definition has to be validated through Huntsman Cancer Institute or a Veterans Affairs Hospital with a repeat PSA test no sooner than 5 days and no later than 14 days from the initial notification of the result demonstrating progression.

OR

Radiographic progression: Any new, progressing, or reappearing lesion on Bone Scan, CT/Scan, or MRI compared to the same scan performed previously. Radiographic Progression will be determined by Prostate Cancer Clinical Trials Working Group (PCWG2) and RECIST 1.1 as described below (section 10.1.1).

* Of note: For a patient to meet radiographic progression criterion for appearance of new bone lesion only, the patient must demonstrate appearance of new bone disease, as confirmed by the treating radiation oncologist, and also meet the biochemical progression definition set out above.

OR

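### For men with fewer than 30 days of bicalutamide, 5.1.2 and the study calendar allow an on-drug baseline PSA, against which 10.1 can later judge biochemical progression

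*Combined protocol and SAP*

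**What the plan says.** - **Stopping bicalutamide (5.1.2).** Men with fewer than 30 days of use are eligible "as long as they discontinue the drug at least 5 days prior to the first study treatment". Men with more than 30 and fewer than 45 days are eligible "providing they have been off of the drug for at least 30 days prior to enrollment".
- **Screening PSA (Section 9, footnote 1).** The footnote refers to "laboratory tests which need to be completed within 2 weeks prior to study enrollment". Section 7.2 adds "The first cycle will commence at study enrollment", so days before enrollment and days before the first dose can be read on one scale.
- **Cycle 1 PSA (Section 9, footnote 13, attached to the PSA and testosterone row).** "All post-screening laboratory tests should be drawn approximately 7 days, but no fewer than 3 business days, before radium dosing".
- **Other hormonal agents.** Section 5.2.7 states: "PSA should not be obtained prior to 30 days after stopping finasteride". Section 5.2.8 has the same rule for dutasteride, with 90 days.
- **Biochemical progression (10.1).** For a baseline above 20 ng/ml with no PSA decrease, "biochemical progression will be defined as a 10% rise over the baseline". For a baseline above 20 with a decrease, it is a rise of more than 10% from the nadir. For a baseline below 20, PSA must exceed 20 and also meet a 10% condition. Progression is measured after EBRT and Cycle 2, and a repeat PSA 5 to 14 days later must confirm it.
- **Consequence (8.1.1).** "Upon confirmed biochemical progression study treatment MUST be discontinued".
- **PSA doubling time (1.2.4)** is also counted from baseline. Neither 1.2.4 nor 10.1 says which pre-treatment draw is the baseline.

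**The concern.** The eligibility rule and the calendar were written separately and do not meet. One fixes when the drug stops, the other fixes when PSA is drawn, and a man can satisfy both while every pre-treatment PSA is taken on an anti-androgen or within a couple of days of stopping it. The plan accepts elsewhere that recent hormonal treatment makes a PSA unsuitable: it sets waiting times for PSA after finasteride and dutasteride, and a 30-day drug-free period for men with somewhat longer bicalutamide use. Only the short-course users have no such safeguard.

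If bicalutamide lowers PSA, the later comparison sets an off-drug value against an on-drug reference with a 10% margin. A return to the man's own untreated level could then be recorded as progression, and confirmed progression ends study treatment. The baseline also decides which of the PSA rules in 10.1 applies to him, and it starts the PSA doubling-time clock.

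**Working it through.** **1. The plan's own power figure.** Inputs from Section 11: 20 evaluable men, 1% versus 20% free of systemic therapy at 15 months, reject if 2 or more are free.

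Power = 1 - 0.8^20 - 20 × 0.2 × 0.8^19 = 1 - 0.01153 - 0.05765 = 0.9308. The exact type I error is 0.0169. The stated 93% reproduces.

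**2. Timing.** Take the last tablet on day -5, the latest that 5.1.2 allows.

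| PSA draw | Source | Relation to last tablet |
|---|---|---|
| Day -14 | footnote 1, earliest | 9 days before |
| Day -7 | footnote 13, nominal | 2 days before |
| Day -5 | footnote 13, later draw | same day |
| Day -3 | footnote 13, latest (3 business days is at least 3 calendar days) | 2 days after |

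At nominal timing both draws are on drug. At the latest timing the Cycle 1 draw is about 2 days off. By contrast, a man in the 30-to-45-day group is at least 30 - 14 = 16 days off drug at screening. Cycle 2 comes at least 28 days after Cycle 1 (8.1.1), so progression is first judged at least 28 + 5 = 33 days off drug. A PSA is drawn around the start of EBRT (footnote 9), but 10.1 does not use it to reset the baseline.

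**3. Suppression needed to cross 10%.** Let the on-drug PSA be (1 - s) times the off-drug level. Returning to that level is a rise of s/(1 - s), which exceeds 10% when s > 1 - 1/1.1 = 9.1%. The documents give no value for s, so the range is assumed.

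| Assumed s | Apparent rise | Multiple of off-drug level at which PSA has doubled from baseline, 2(1 - s) |
|---|---|---|
| 5% | 5.3% | 1.9 |
| 10% | 11% | 1.8 |
| 20% | 25% | 1.6 |
| 30% | 43% | 1.4 |
| 50% | 100% | 1.0 |

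**4. Who can be misclassified under 10.1.**

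- *On-drug baseline above 20, no PSA fall on treatment.* Any s above 9.1% is enough.
- *On-drug baseline below 20, off-drug level above 20.* Returning to the off-drug level crosses 20. Assumed example: 15 on drug and 22 off drug, a rise of 22/15 - 1 = 47%. With an off-drug baseline of 22 and no fall, he would have needed 22 × 1.1 = 24.2.
- *Off-drug level 20 or less.* Washout alone cannot meet the definition, whatever s is.
- *Baseline above 20 with a fall.* The nadir is the reference. Washout matters only if the nadir itself is still drug-affected, on which the documents give nothing.

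PSA doubling time has no 20 ng/ml condition, so the last column of the table in step 3 applies to every such man.

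**5. Primary endpoint.** Suppose m of the 20 men are wrongly counted as failures, a worst-case illustration. Power is then the probability of at least 2 successes among 20 - m men at 20%: 91.7% for m = 1, 90.1% for m = 2 and 85.9% for m = 4.

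**6. Evaluability.** Section 10 requires at least 3 Radium-223 cycles. A man stopped after Cycle 2 has had 2, so he may leave the evaluable set instead of counting as a failure.

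**The case against.** Several stronger readings are tempting, and the documents do not support them.

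- *Any return to the off-drug PSA counts as progression.* It does not. With a baseline below 20, PSA must also exceed 20. The one comparable figure in Section 2 is a median initial PSA of 5.4 in a 40-patient SBRT trial in bone-only metastatic prostate cancer. That is another trial, but it suggests that men above 20 may be few.
- *The 9.1% threshold applies to everyone.* It decides the matter only for a baseline above 20 with no fall on treatment.
- *The rebound is a fact that the repeat test will confirm.* The size, onset and duration of PSA suppression are not in the documents. What can be said is that a second draw 5 to 14 days later does not remove a sustained rise.
- *The primary endpoint is biased.* Its event is the start of ADT. Section 8.1.1 requires study treatment to stop but does not require ADT, and 7.4 keeps progressed men in follow-up. Objective 1.1.1 does speak of ADT for progression, so the link is plausible, but it is indirect.
- *The Cycle 1 PSA is always on drug.* A man may stop earlier than day -5, and a late draw can fall after the stop.

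These points limit the harm, but they leave the gap in the rules untouched.

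**Conclusion.** The point holds as a gap in the stated rules: a fully compliant man can enter with no off-drug baseline PSA, and 10.1 has nothing that excludes or resets it. That much needs no outside assumption.

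The consequences are conditional. Misclassified biochemical progression requires an off-drug PSA above 20 ng/ml and, where the baseline is above 20 without a fall, suppression above 9.1%. The effect is direct on biochemical progression, the treatment stop in 8.1.1, PSA doubling time and the exploratory biochemical progression-free survival correlates. On the primary endpoint it is indirect and probably small: 1.4 percentage points of power for one man wrongly counted as a failure. One such man would reverse the conclusion only if exactly 2 of 20 would otherwise have been free of systemic therapy.

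A reader might infer that the error always works against the treatment. Through the event count it does, without raising the type I error. Through the evaluability rule, a likely failure may leave the denominator, which flatters the result, so the net direction is not fixed. The number of men using the under-30-day allowance is not given and could be zero. This should be corrected, but it does not undermine the design.

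**What to change.** 1. Reconcile 5.1.2 with footnotes 1 and 13 of the calendar and with 10.1.
2. State which PSA is the baseline for 10.1 and 1.2.4.
3. For men with recent bicalutamide use, require that this baseline is not an on-drug value, with a PSA-timing sentence of the kind already in 5.2.7 and 5.2.8. The interval is for the sponsor to set.
4. Where no such draw exists, use the most recent PSA taken before bicalutamide was started. The sponsor should set an age limit for it: 5.1.1 enrolls men with rising PSA, and an old, lower value would make a 10% rise easier to reach and recreate the problem.
5. Pre-specify a sensitivity analysis of biochemical progression and PSA doubling time that re-baselines or excludes these men, and report how many there were.

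This concerns which measurement serves as the reference. It proposes no change to the drug-free period or the treatment schedule. The cost is a sentence in 5.1.2, a definition in 10.1 and a calendar footnote. For a few men an earlier PSA may have to be retrieved from the records, and it may be slightly out of date.
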